The primary objective of the economic evaluation is to estimate the cost-effectiveness and cost-utility of CLI treatment versus DBS treatment in the first year of follow-up after treatment initiation. The results of the cost-effectiveness analysis (CEA) allow for local decision making on the economically most optimal treatment approach for patients with PD, based on the clinically relevant health outcomes regarding quality of life in particular, while the cost-utility analysis (CUA) provides information for health policy decision makers to decide upon efficient and affordable health care in general, based on nationally accepted evaluation criteria regarding costs per QALY in view of patients' disease burden.

Types of economic evaluation

The economic evaluation of CLI against DBS was conducted alongside the INVEST clinical trial with individual patient-level data. The costs per unit change on the PDQ-39 summary index score at 12 months follow-up versus baseline and the costs per quality adjusted life year (QALY) were the primary economic outcomes. Incremental cost-effectiveness (ICER) and cost-utility (ICUR) ratios were calculated as the costs difference divided by the difference in effect for CLI minus DBS treatment.

Jurisdiction

The trial was conducted in the Netherlands, where health insurance is obligated for inhabitants and health care is offered by public and private providers.

Perspective, time horizon and discounting

Both health care and societal perspectives were taken into account with a time horizon of 12 months following index surgery. Because the time horizon was 12 months, no discounting was performed.

Cost components

Costs encompassed health care costs, out-of-pocket expenses by patients and family members and costs of productivity loss due to sick leave from work (absenteeism) or lowered efficiency while at work (presenteeism).

Sources

Health care costs covered the use of the following use of resources:

- screening for appropriateness of treatment indication;
- index treatments CLI with infusion devices or DBS with stimulation devices;
- emergency departments visits;
- inpatient hospital admissions at neurology, psychiatry, the intensive care, or other units;
- outpatient hospital consultations (*e.g.*, medical specialist, specialist nurse);
- diagnostic procedures (*e.g.*, imaging by MRI, CT, ultrasonography or X-ray);
- therapeutic procedures (*e.g.*, ex-plantation, revision tube or other material, medication);
- out-of-hospital consultations (general practitioner, physical therapist, psychologist, other);
- institutionalized care (*e.g.*, nursing home, rehabilitation center);

- formal home care (e.g., housekeeping, personal care, nursing);
- use of medication.

Out-of-pocket expenses included the following used resources:

- over-the-counter medication;
- informal help at home;
- non-reimbursable devices;
- health-related travel;
- additional expenses by informal primary caregivers.

Productivity loss focused on the impact of CLI and DBS on lost working hours from paid work only and was addressed exploratory. Lost working hours in the subgroup of patients with a paid job were quantified by summing the:

- number of days of sick leave multiplied with patient's mean number of working hours a day;
- number of affected days at work multiplied with the factor "(10 minus self-reported efficiency)/10" with self-reported efficiency reported on a scale from 0 (did not accomplish anything at all) to 10 (worked as efficiently as always).

Lost working hours in the subgroup of primary caregivers with a paid job were estimated as supplied by those caregivers.

Data on use of health care resources were derived from hospital records, electronic clinical report forms and the Medical Consumption Questionnaire (iMCQ) completed by patients or their primary caregiver at quarterly intervals.²² The questions on the out-of-pocket expenses presumed relevant were added to the iMCQ. To quantify health-related travel, the numbers of contacts with distinct health care providers were counted and combined with standardized distances in kilometers between patients' homes and local health care providers,²³ except for the geographically more thinly scattered DBS treatment centers in which case the mean of the actual distances in kilometers between postal codes of providers and patients were used.²⁴ The result per patient was multiplied by two considering the 'to and from' of traveling. Data on sick leave from work and lowered efficiency while at work from patients as well as lost working hours by the primary informal caregiver were gathered with an adjusted version of the Productivity Costs Questionnaire (iPCQ).²⁵

Unit costs and costing

If opportune, unit costs of (non-)hospital resources, working hours lost, and time spent on the patient by the primary care-giver were obtained from the most recent Dutch Manual on Costing in health care research (DMC).²³ The unit costs of the (re)placement of the neurostimulator system and of the tube and pump system (re)placements were based on unit costing sheets for distinct hospital care resources from the treatment center with the highest number of inclusions and subsequently capitalized based on a 5-year depreciation period (reflecting the lengths of their life cycles) in order to allow for a robust estimate of the difference in yearly treatment costs by study arm, irrespective of the chosen study's time horizon. The same hospital unit costing sheets, existing rates for mutual services excluding VAT, or passer-by prices (e.g., AMC Passantenprijslijst OZP, 2020) were used for observed diagnostic examinations and therapeutic procedures not listed in the DMC. Unit costs for medication were gathered from the Dutch Pharmaceutical Compass assuming standard prescriptions.^{26,27} The unit cost of lost working hours at the mean age of the included working patient at baseline was used, non-specific for gender. In case of prolonged continuous sick leave longer than the friction period, the friction cost method was applied.²⁸ The length of the friction period in days was calculated as the average over the study's observation period 2015-2020, weighted for the

yearly number of included patients, and equaled 97 days.^{23,29} Table EE1-S in the Supplementary Material shows unit cost of the resources used. Unit costs held for the base year 2020; unit costs originating from different calendar years were price-indexed with general yearly consumer price indices from Statistics Netherlands.³⁰

Costs of resources used were calculated by multiplying the frequency of distinct resources used with their respective (depreciated) unit costs. Volumes and costs (of health care used, out-of-pocket expenses, and productivity loss) are reported separately as (subtotal and total) means per patient per study arm.

Analyses were adjusted if deemed necessary in case of Parkinson-related or Parkinson non-related outliers in costs or QALYs. If related to Parkinson's disease, these were included and reported, if caused by unrelated comorbidities, these could have been excluded.

Health outcomes

The primary health outcome in the cost-effectiveness analysis was the change in the PDQ-39 between baseline and 12 months after randomization. The change score showed the increase or decrease in number of difficulties across eight different dimensions of health (including mobility, activities of daily living, emotional well-being, and stigma) as experienced by patients in the preceding month. Dimension scores are coded on a scale of 0 (perfect health as assessed by the measure) to 100 (worst health as assessed by the measure). The change score was defined as the mean score on the eight scales at month 12 minus the mean score at baseline, in theory ranging from -100 to +100 with a score of 0 representing 'no change'.

The primary health outcome in the cost-utility analysis was the number of QALYs. Patient's health status was assessed with the EQ-5D-3L at baseline, one week, three months, six months, nine months, and 12 months post randomization. The EQ-5D contained five items: mobility, self-care, usual activities, pain/complaints, and mood (anxiety/depression).³¹ Each item had three response options: no problems, some problems, or serious problems. EQ-5D scoring profiles at successive measurements were converted into health utility scores using general population based tariffs of time trade-off ratings of health states.³² QALYs were calculated by taking the product sum of the health utility scores during follow-up and the interval lengths in years in-between successive measurements.

Health economic analysis methods

Analysis population

The CEA and CUA were done with the modified intention-to-treat population (see page 9) with references to the CONSORT-flow diagram in Figure SAP-1 and the baseline characteristics of the two RCT-subpopulations in Table EE1. Summary statistics for health utility scores at baseline were included in the manuscript text.

Cost-effectiveness threshold

The applied cost-effectiveness threshold for the sample size calculation was €120,000 as described and substantiated in the published study protocol.¹

Statistical decision rules

Use of resources by patients were counted by type of resource by treatment group and summarized as means per patient with 95% bias corrected and accelerated confidence intervals (95% BCa CI) after non-parametric bootstrapping, drawing 2,500 samples of the same sizes as the original samples and with replacement (see Tables EE2a on hospital resources and EE2b on out-of-hospital resources and productivity loss). The associated costs of these used resources were summarized similarly, at the same disaggregated level and reported in the Supplementary Material in Tables EE3a-S and EE3b-S. Health-related out-of-pocket expenses by patients and their families were added to EE3b-S. Mean per patient costs per treatment group at aggregated level and the corresponding group differences were reported in Table EE3 in the main manuscript, along with P-values. Differences in mean aggregated costs were assessed using two-sample *t*-tests applying the abovementioned non-parametric bootstrapping procedure for 95% BCa CIs.

In addition to the clinically reported (differences in) changes from baseline in PDQ-39, the mean QALYs per patient per treatment group and the mean difference were assessed using two-sample *t*-tests applying the abovementioned non-parametric bootstrapping procedure for 95% BCa CIs.

Data cleaning

Source validation was performed by independent monitoring and related queries were solved by [name]. Inconsistencies in patient reported data on outcomes and use of resources were solved and registered by syntax ([name]). If appropriate, skipped questionnaire items due to routing were set to a zero score, again registered by syntax ([name]). Reported counts of resource use by follow-up time were checked for crossing acceptable ceiling levels (*e.g.*, 77 hours of informal care or 77 hours of work a week, allowing for 7 * 11 hours of rest a day plus 14 hours anywhere in between to have at least one consecutive period of 36 hours rest a week).³³

Handling of missing data

Missing PDQ-39 outcome data were handled in accordance with the clinical analyses based on separate treatment groups (see page 10). Patients who died were assumed to generate zero QALYs and zero costs beyond the time of death.

For missing health utility data over time among patients alive and for missing data on resource use during follow-up the choice of imputation approach depended on the observed missing data pattern and whether or not missingness was associated with baseline variables or previously observed outcomes. Missingness of data (completely) at random was handled with multiple imputation as described above (see page 10).

In a sensitivity analysis potential missingness of data not at random was addressed to account for the expectation by the treating clinicians that missingness of data may well depend on a worsened health status (see also page 10). The following scenarios were addressed in this sensitivity analysis by shifting the costs and health outcomes from the missingness (completely) at random imputation:

- a) increasing actually imputed costs by 20% and 40%
- b) increasing actually imputed PDQ-39 summary index scores changes by 20% and 40%
- c) decreasing actually imputed QALYs by 20% and 40%
- d) combining a) and b)

e) combining a) and c).

Findings of the clinical analyses might have suggested to explore additional scenarios for the sensitivity of the economical evaluation. The higher its impact, the more extensively the sensitivity analysis was reported in the main text, with the remainder reported in the Supplementary Material.

The handling of missing data applied recommendations by Faria et al.³⁴

Cost-effectiveness

Incremental analysis

Differences in costs and differences in changes in PDQ-39 from baseline between the treatment groups were used to calculate the incremental cost-effectiveness ratio (ICER), again following non-parametric bootstrapping drawing 2,500 samples of the same sizes as the original samples and with replacement to account for sampling variability. Likewise, differences in costs and differences in QALYs were used to calculate the incremental cost-utility ratio (ICUR). Differences in costs and the associated differences in health outcomes were plotted with cost-effectiveness planes,³⁵ for example see Figure EE-1.

For each of the 2,500 bootstraps the net health benefits (NHB) of CLI versus DBS were calculated based on the ICERs for different levels of willingness-to-pay up to €3,000 per additional unit decrease in change in PDQ-39 (NHB_{PDQ-39}), respectively based on the ICURs for willingness-to-pay levels up to €160,000. Cost-effectiveness acceptability curves were plotted to represent uncertainty,³⁶ showing the probability of CLI being cost-effective in comparison with DBS at each level of willingness to pay, see Figure EE-2.

Subgroup analyses

Considering the limited patient numbers, potentially uneven distributions of baseline characteristics despite randomization were exploratory addressed by subgroup analyses for hypothesis generation. Also, a preplanned subgroup analysis by median age was performed to detect a potential influence of being more vulnerable at a higher age.

Additional sensitivity analyses

Apart from addressing the uncertainty of missing data structures, additional sensitivity analyses were performed for the lengths of the life cycles of the DBS and CLI equipment and corresponding depreciation period (6 to 8 years in steps of 1 year versus 5 years).

Scenario analyses

A scenario analysis for the ICUR was performed to correct for health utility scores at baseline by subtracting for each patient the baseline score from the calculated QALYs during the follow-up of 12 months. Another scenario analysis was done to report the ICUR from an international perspective by applying the time trade-off based on valuation of health states based on preferences from the UK general population to the EQ-5D-3L health status profiles and conversion of Euros into English Pound by applying purchasing power parities from the Organisation of Economic Cooperation and Development (or 0.688 divided by 0.772 in 2020).^{37,38}

Table EE2a. Mean per patient use of hospital resources by strategy*

	CLI (n=)	DBS (n=)	Difference** CLI vs DBS
	Mean (95% BCa CI)	Mean (95% BCa CI)	Mean (95% BCa CI)
Screening for suitability			
preop. outpatient consultation			
inpatient stay			
on-/off-phase evaluation			
evaluation / nasogastric tube			
vitamin examinations			
other laboratory			
preop. anesthetic evaluation			
EKG			
MRI-brain	NA		
Continuous Levodopa Infusion			
CLI-pump			
CLI-cassettes			
PEG-jejunostomy placement			
tube replacement			
Deep Brain Stimulation			
(re)implantation			
electrode replacement			
extension cable replacement			
battery exchanges			
Other hospital care			
Emergency department visit			
Hospital stay (in days)			
neurology ward			
psychiatric ward			
intensive care unit			
other			
Outpatient consultation			
neurologist			
CLI/DBS-nurse			
neurosurgeon			
gastroenterologist			
PEG-nurse			
psychiatrist			
(neuro)psychologist			
Imaging diagnostics			
MRI brain			
CT brain			
X-ray DBS leads			
CT abdomen			
ultrasonography abdomen			
Therapeutics			
ex-plantation (battery, lead,...)			
related medication			

BCa CI: bias corrected and accelerated confidence interval, CLI: continuous levodopa infusion, CT: computed tomography, DBS: deep brain stimulation, EKG: electrocardiogram, MRI: magnetic resonance imaging, NA: not applicable, PEG: percutaneous endoscopic gastrostomy

*P-values not reported for use of resources

**Differences rounded to zero keep their sign

Table EE2b. Mean per patient use of non-hospital resources and productivity loss by strategy*

	CLI (n=)	DBS (n=)	Difference** CLI vs DBS
	Mean (95% BCa CI)	Mean (95% BCa CI)	Mean (95% BCa CI)
Non-hospital care			
Medication			
CLI-cassettes related medication			
Out-of-hospital consultation			
general practitioner			
occupational therapist			
physiotherapist			
speech therapist			
dietician			
social worker			
psychologist			
rehabilitation physician			
company physician			
Other institutional stay			
nursing home day			
rehabilitation center day			
Formal home care			
house holding			
personal			
home nursing			
Equipment			
walking devices			
other living aids			
Productivity loss in hours			
absenteeism			
presenteeism			

BCa CI: bias corrected and accelerated confidence interval, CLI: continuous levodopa infusion, DBS: deep brain stimulation

* P-values not reported for use of resources

** Differences rounded to zero keep their sign

Table EE3. Mean per patient costs by strategy

	CLI (n=)	DBS (n=)	Difference* CLI vs DBS	P-value
	Mean costs (95% CI)	Mean costs (95% CI)	Mean costs (95% CI)	
Hospital care				
Screening for suitability				
Continuous Levodopa Infusion				
Deep Brain Stimulation				
Emergency department visit				
Hospital in patient stay				
Outpatient consultation				
Diagnostics				
Therapeutics				
Non-hospital care				
Medication				
Out-of-hospital consultation				
Other institutional stay				
Formal home care				
Equipment				
Out-of-pocket expenses				
Productivity loss				
Total health care costs				
Total societal costs				

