dyskinesias, and sleep states). The patients will have an assessment containing the MDS-UPDRS and the AMC Linear Disability Score (ALDS) in standardized OFF and ON phases. The OFF phase is defined as the condition of the patient after withholding PD medication for 12 h and being awake for at least 1 h. The ON phase is the condition 1 h after a supra-threshold levodopa dose. The supra-threshold levodopa dose is based on the patient's usual first morning dose of PD drugs. To calculate the supra-threshold levodopa dose, different drugs will be pooled in Levodopa Equivalent Doses. The standardized OFF and ON phases examination will be videotaped. In the ON phase the patient will also undergo documentation of the Non Motor Symptom Checklist, Parkinson's Disease Impulsive-Compulsive Disorders Questionnaire, Hoehn and Yahr stage, ALDS, Rotterdam Symptom Checklist, Clinical Diskinesias Rating Scale (CDRS), patient-reported perceived quality of life (PDQ-39), EuroQol-5D (EQ-5D), iMTA Medical Consumption Questionnaire (iMCQ), iMTA Productivity Cost Questionnaire (iPCQ), use of (informal) care, apathy assessed by researcher and caregiver, caregiver burden and preference for treatment. The trial nurse will also administer the Mini-International Neuropsychiatric Interview (MINI) [20] and the Columbia Suicide Severity Rating Scale to screen psychiatric morbidity. The patients will undergo a neuropsychological examination including the Mattis Dementia Rating Scale and the Parkinson's Disease Cognitive Rating Scale (PD-CRS) and Patient-reported outcome tool for advanced Parkinson's disease (PROAPD) and a standardized psychiatric assessment.

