After baseline screening, patients eligibility for both treatments will be discussed with the appropriate disciplines (neurology, neuropsychology, neurosurgery, and gastroenterology) in the treating centre, or the centre that will provide the treatment. If any possible contraindications for one of the treatments is found, the patient will be excluded from the study. Possible contra-indications are a non-dopamine responsive tremor as main complaint or if the effect of dopaminergic medication on motor symptoms is too small. Subsequently, the patient is randomized using a web-based application. Dependent on the result of randomization, the patient will be treated in the own hospital or he or she will be referred to one of the cooperating DBS centres. Within 3 months after the baseline assessment the study-treatment — DBS or CLI — will be started. The treatment will be performed as described in section 5.1

At visits 2, 3, 4, 5, 6, 7 and 8 patients will undergo documentation of PD-medication, adverse events (through a standardized questionnaire), treatment failure and cross-over. The iMCQ, iPCQ, use of (informal) care and caregiver burden are assessed at visit 3, 4, 5, 6, 7 and 8. At visits 5, 6, 7 and 8 we will record the PDQ-39. At visit 6, 7 and 8 the patients

Version 7: 23-10-2019 25 of 48

will keep a motor symptom diary (3 days; including ON/ OFF phases, dyskinesias, and sleep states) and the Non Motor Symptom Checklist, ALDS and patient satisfaction with the treatment. At visit 6 we will record the MDS-UPDRS, the CDRS and blood analysis as described above will be repeated. Also, patients will undergo a short neuropsychological examination and standardized psychiatric assessment at visit 6 and 8. The first year of follow-up, a margin of one month is deemed acceptable in planning a visit, for the second and third year of follow-up, the visits will be completed within two months of the defined follow-up date.

Patient preference trial

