8.8 Secondary study parameter(s)

RCT

The main clinical analysis of the study consists of a comparison between the trial treatment groups (DBS versus CLI) of the primary clinical outcome (PDQ-39) 12 months after the start of the study treatment. First, the follow-up difference between PDQ-39 scores will be analysed using a two-group t-test. Second, the PDQ-39 follow-up scores will be further investigated using multiple linear regression taking into account patients' PDQ-39 baseline values, the stratifying variables (experience of the including centre with DBS and CLI; response to Levodopa) and (if necessary) for clinically relevant baseline imbalances. Additionally, the repeated data structure will be investigated with a linear mixed model. The same analyses will be performed for the 24 and 36 month outcomes. With regard to the comparisons of the other secondary outcomes PD motor symptoms (MDS-UPDRS, CDRS, 3-day motor symptom diary), non-motor symptoms such as autonomic functions and sleep (Non Motor Symptom Checklist, Rotterdam Symptom Checklist), PD-medication, neuropsychological and psychiatric assessment, disability, functional health status (ALDS), patient and physician preferences, patient satisfaction, adverse effects and complications, treatment failure, stopping treatment, starting with the alternative than initially started treatment, caregiver burden and medical and non-medical care costs (iMCQ, iPCQ) we will use the appropriate parametric and non-parametric statistics. In all analyses, statistical uncertainties will be expressed in 95% confidence intervals.

Patient preference trial

As mentioned before a patient preference observational study will be conducted to asses external validity of the randomized controlled trial results. The primary clinical outcome of the non-randomized group and randomized group will be compared using the two-group t-test and linear regression, whereas baseline characteristics will be compared with the

Version 7: 23-10-2019 32 of 48

two-group t-test and Chi-square test, when appropriate. Finally, the impact of the treatment on the PDQ-39 follow-up scores of the randomized and non-randomized group will be analysed using multiple linear regression, adjusting for relevant imbalanced baseline variables and randomized status (agreeing to randomization or not).

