9.5 Incentives (if applicable)

Patients will not receive incentives or privileges to participate in this study. Most DBS-centres have a waiting list for treatment with DBS whereas treatment with CLI can be initiated at a relatively short notice (within 3 months). For optimal comparison of the therapies, in patients who participate in the study, start of treatment will be within three months of the baseline screening. This may be a motivation for patients to participate in the study. We do not expect that the waiting list for treatment with DBS will grow for patients not taking part in the study, as a proportion of patients that would otherwise be treated with DBS, will now be randomized for treatment with CLI.

Version 7: 23-10-2019 36 of 48

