Originally, an intention-to-treat analysis (ITT) was planned as the primary analysis. Nevertheless, during the study it was observed that after allocation, several patients immediately refused CLI treatment and either chose to be treated with DBS or quitted study participation. Analyzing these patients in an ITT could have introduced a significant bias, as their apparent preference for DBS made them not representative of a population that considered CLI a suitable treatment for advanced PD. Furthermore, for the patients for whom post-baseline data were not available, all these data would have had to be imputed, contributing to the risk of bias. A modified intention-to-treat (mITT) population was introduced as the primary analysis, because analysis in the ITT population including all randomized individuals was considered less valid.⁷ The mITT population included all randomized patients who received the allocated treatment and continued in the RCT after randomization. Additionally, in line with the proposed strategy for ITT analyses for trials with incomplete outcome data as proposed by White et al.,⁷ sensitivity analyses were performed to explore the robustness of the main analyses in the mITT population and included analyses in all randomized patients (the ITT population). Please see “Sensitivity analysis” for details on page 12.

While conducting the study, it was observed that comorbidities had a negative impact on completeness of the follow-up data. To assess for a possible bias towards a selective data collection of healthier patients, treating physicians of patients that had dropped out of the study were contacted to obtain additional information on the general health status and level of functioning of these patients. Please see also “Patient replacement and missing data” on page 10.

Study methods

Outcomes - randomized controlled trial

Primary outcomes

The main clinical outcome was the change from baseline to 12 months after initiation of treatment in PDQ-39 (score 0-100).⁸

The primary health economic outcomes are elaborated on page 19.

Secondary outcomes

- PD motor symptoms -- Movement Disorder Society’s Unified Parkinson’s Disease Rating Scale (MDS-UPDRS) part III in on-drug state (score range 0-132) ²;
- Motor experiences of daily living-- MDS-UPDRS part II in on-drug phase (score range 0-52) ²;
- Dyskinesia -- Clinical Dyskinesia Rating Scale (CDRS, score range 0-28) in on-drug state ⁹;

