For normally distributed data means and standard deviation were presented, for non-normally distributed data medians and interquartile ranges. For the Hoehn & Yahr stage median and range were reported.

Analyses

Randomized controlled trial

Reported outcomes were presented in Table SAP2 (part A and B). The main publication consisted of analyses in the mITT population. The analyses in ITT, as-treated and per-protocol populations were presented in supplements.

Analysis of main clinical outcome

The main analysis regarding the clinical outcome was the between-group difference in change from baseline to 12 months follow-up in total PDQ-39 summary index score in the mITT population, using a two-group *t*-test. Additionally, a multiple linear regression analysis was performed taking into account the stratifying variable (level of experience of the treatment center) and (if necessary) clinically relevant baseline imbalances. To assess whether the baseline value of the PDQ-39 served as an effect modifier (meaning that the association between intervention and outcome differed according to baseline PDQ-39) an interaction term was used in the regression analysis. In case of a significant interaction term, the analysis was additionally performed in two separate strata: one with patients with a median PDQ-39 or below and the other with patients with a PDQ-39 above median.

Sensitivity analyses

Sensitivity analyses concerning missing data as described in the paragraph “Patient replacement and missing data” were performed in the mITT population. To further assess robustness of the mITT analysis for the main clinical outcome additional sensitivity analyses were performed.

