Since DBS treatment through usual care was restricted with a long waiting list, it was expected that some patients hoped to receive this treatment sooner through study participation. It was an anticipated unwanted scenario that some patients therefore would decline allocated treatment after randomization, because of a strong preference for the other treatment. This would be considered a protocol violation and made patients ineligible for the modified intention to treat population.

[figure not shown]
Missing of 12-month follow-up visit

Missing the 12-month visit would have resulted in significant incompleteness of data. Since this would probably not have been at random, this could have affected integrity of analyses. Therefore, this visit was deemed indispensable and missing it was considered a protocol violation.

Migration from the RCT to ancillary patient preference observational study population

If a patient found participation in the RCT too burdensome after receiving allocated treatment, continuation of study participation was encouraged. If a patient crossed-over to the ancillary patient preference arm, this was deemed a violation from the RCT protocol.

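### Treatment preference is recorded before randomisation but the SAP and HEAP do not use it, while the mITT rule in practice removes DBS-preferring refusers from the CLI arm only

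*SAP*

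**What the plan says.** **Preference is measured before allocation.** Protocol section 7.3 ends its list of baseline questionnaires with "caregiver burden and preference for treatment", and the assessment schedule in appendix 12.4 places it at visit 1 only. Eligibility is then discussed. "Subsequently, the patient is randomized using a web-based application".

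**Access to DBS is an acknowledged motive.** Protocol section 9.5 notes that most DBS centres have a waiting list, whereas study treatment starts within three months of baseline. It adds: "This may be a motivation for patients to participate in the study". SAP Appendix I, under refusal of allocated treatment, says "it was expected that some patients hoped to receive this treatment sooner through study participation".

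**Refusers leave the primary population.** The SAP's synopsis of protocol development reports that several patients refused CLI immediately and either took DBS or left the study. It excludes them because "their apparent preference for DBS made them not representative of a population that considered CLI a suitable treatment for advanced PD". The rule under Analysis populations is neutral between arms: a patient must have received the allocated treatment.

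**Analyses.** The SAP regression for PDQ-39 is described as "taking into account the stratifying variable (level of experience of the treatment center) and (if necessary) clinically relevant baseline imbalances". ITT, as-treated and per-protocol analyses of PDQ-39 are planned as sensitivity analyses. The HEAP's Analysis population section uses mITT for both the cost-effectiveness and the cost-utility analysis.

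**The concern.** The SAP's reason for exclusion is a statement about a population: people who do not find CLI suitable should not inform the comparison. By randomisation, about the same share of such people should sit in each arm. Refusal reveals them only in the arm that received the unwanted allocation, so the principle is applied to one side. The primary contrast then compares CLI patients who accept CLI with DBS patients of whom some would have refused it.

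This matters because the trial is open label and both PDQ-39 and EQ-5D are self-reported. Patients who got the treatment they hoped for may report more improvement. If so, the DBS arm keeps more of them, and the comparison mixes treatment effect with satisfied preference. The same population carries the QALY and cost comparison, which is the trial's primary question.

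**Working it through.** **1. The plan's own figures reproduce.** Inputs from protocol section 4.4: QALY difference 0.2847, QALY SD 0.35, cost SD €10,000, willingness to pay €120,000, two-sided alpha 0.05, power 80%, dropout 20%.
- SD of net health benefit at zero correlation: √(0.35² + (10,000/120,000)²) = 0.3598.
- n per group = 2 × (1.960 + 0.842)² × 0.3598² / 0.2847² = 25.1, so 26 (exact t-test solution 26.07).
- 26 / 0.8 = 32.5, so 33 per group and 66 in total.
- Detectable PDQ-39 difference at 26 per group and SD 15: 11.89, against the stated 11.9.

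No arithmetic error is involved; the issue is selection.

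**2. What the one-sided removal does.** Let p be the share of patients who would refuse CLI, equal in expectation in both arms. Let d be the extra PDQ-39 improvement that such patients report on DBS compared with other DBS patients.
- mITT mean improvement, CLI arm: acceptors only.
- mITT mean improvement, DBS arm: (1 − p) × acceptors + p × would-be refusers = acceptors + p × d.
- Contrast: the effect among acceptors, plus p × d in favour of DBS.

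With k refusers of 33, the bias is k × d / 33. The documents say only that several patients refused, and they give no preference effect. Both k and d, including the sign of d, are therefore assumptions.

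| k of 33 | share | d = 5 | d = 10 | d needed to reach 1.6 (52.8 / k) |
|---|---|---|---|---|
| 3 | 9% | 0.45 | 0.91 | 17.6 |
| 4 | 12% | 0.61 | 1.21 | 13.2 |
| 5 | 15% | 0.76 | 1.52 | 10.6 |
| 6 | 18% | 0.91 | 1.82 | 8.8 |
| 7 | 21% | 1.06 | 2.12 | 7.5 |

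The 1.6 benchmark is the minimal clinically important difference in the SAP's missing-data section. Within this grid it is reached only with 6 or 7 refusers and a gap of at least 8.8 or 7.5 points. A wider grid (2 to 10 refusers, 5 to 15 points) runs from 0.3 to 4.5 points.

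**3. Power is a minor matter.** With 20% other dropout (26 DBS patients and (33 − k) × 26/33 CLI patients), power for 0.2847 QALY goes from 79.9% to 77.9% with 3 removed and 73.6% with 8 removed.

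**4. Where the SAP and HEAP could have used preference.** It is absent from the outcome lists, the named imputation predictors (given only as examples), Table SAP1, the named covariates, the sensitivity analyses and Table SAP1-S. The HEAP's only preplanned subgroup is median age.

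**5. Do the planned sensitivity analyses cover it?**
- ITT for PDQ-39: yes in part. It restores every randomised patient, but outcomes of those who quit must be imputed, which the SAP itself names as a bias risk.
- As-treated: no. A patient who refused CLI and took DBS is counted under DBS, which adds DBS-preferring patients to that arm.
- Per protocol: no. Refusal is listed as a violation, so the same exclusion applies.
- Economic outcomes: mITT, with no ITT version specified.

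**The case against.** The strongest reply has four parts.

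*Preference is not ignored.* A reader might infer that it is never used anywhere. The documents do not support that: protocol section 7.1.2 lists patient and physician preferences as a secondary parameter, and section 8.8 includes them among the outcomes to be compared ("disability, functional health status (ALDS), patient and physician preferences, patient satisfaction, adverse effects and complications, treatment failure"). The SAP's clause on baseline imbalances, and the HEAP's exploratory subgroups for uneven baseline characteristics, could also admit it. This stands as a limit on the claim. But comparing an item is neither restriction nor adjustment, and no planned baseline table would reveal an imbalance in preference.

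*Safeguards exist.* The ITT analysis treats both arms alike without any preference variable. The SAP also compares randomised patients with those who chose the same treatment. The first is a real check for PDQ-39. The second is non-randomised and concerns external validity. Neither is specified for costs and QALYs; the HEAP leaves room for further scenarios but does not name an ITT run.

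*Enrichment is not shown.* The documents say that access may motivate and that some patients hoped for faster DBS; they do not say how many. The protocol's survey of 62 orally treated patients found 40% preferring CLI and 9% DBS, while its own estimate for the preference arms is 60% DBS. So the extent is unknown.

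*The assumed bias is small beside sampling error.* At SD 15 and 33 per arm, the standard error of the difference is 15 × √(2/33) = 3.7 points, so 0.5 to 2.1 points is about 0.1 to 0.6 standard errors. That is fair, but a systematic shift is not reflected in the confidence interval.

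**Conclusion.** The concern holds in a limited form. Preference is recorded before randomisation but not used in the SAP or HEAP. The primary population in practice loses patients who reject CLI for DBS from one arm, and the primary economic outcomes have no specified ITT check.

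Two stronger readings should be resisted. The mITT rule is not directed at CLI: someone who refused DBS would be excluded too, and the asymmetry lies in the refusals described. Nor does the rule strip the CLI arm of DBS-preferring patients, because those who accepted CLI remain.

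The bias of 0.5 to 2.1 PDQ-39 points rests wholly on assumed inputs (3 to 7 refusals, a gap of 5 to 10 points, and a gap that favours DBS). It may be unimportant, but the plan as written gives no means of telling. This is a worthwhile, inexpensive improvement, and it does not invalidate the trial.

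**What to change.** 1. **Describe.** Add baseline treatment preference to Table SAP1 by arm, for all randomised patients and for the mITT population.
2. **Restrict both arms alike.** Prespecify one sensitivity analysis of PDQ-39, costs and QALYs that starts from all randomised patients and excludes those with a stated baseline DBS preference from both arms, in place of exclusion by refusal. Use the planned imputation for any missing outcomes.
3. **If a regression is used,** include preference and its interaction with treatment, labelled exploratory. A main effect alone assumes that preference acts equally in both arms, and so does not remove an effect that arises only when patients receive what they wanted.
4. **Economic outcomes.** Add an ITT run of the cost-effectiveness and cost-utility analyses.

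The cost is SAP and HEAP wording plus a few extra runs on data already scheduled for collection. There are three drawbacks. The restricted set is smaller and less precise, because it also drops DBS preferrers who accepted CLI. Refusers with no stated DBS preference come back in, and some will need imputation. The analysis also depends on how preference was coded, which the documents do not state; the SAP should give the categories.
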